9.4.4 SAFETY ANALYSES

Serious adverse device events for both cohorts will be presented. Any adverse events occurring during any phase of the study judged by clinical site primary investigators (PIs) to be related to the device will be recorded and presented in a listing using the safety population. A tabular summary of adverse events by system organ class and preferred term will also be provided using the safety population. The severity of each event will be evaluated by the site PI and presented in the listing and table.

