8.2 SAFETY AND OTHER ASSESSMENTS

Safety assessments will include the evaluation of adverse device events (ADEs).

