8.3 ADVERSE DEVICE EFFECTS, SEVERITY, AND REPORTING

8.3.1 DEFINITION OF ADVERSE DEVICE EFFECTS (ADE)

An ADE is an adverse event related to the use of an investigational medical device. This includes any adverse event resulting from insufficiencies or inadequacies in the instructions for use, the deployment, the implementation, the installation, the operation, or any malfunction of the investigational medical device. This also includes any event that is a result of a user error or intentional misuse.

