8.3.4.2 RELATIONSHIP TO STUDY TREATMENT

All ADEs must have their relationship to study treatment assessed by the clinician who examines and evaluates the participant based on temporal relationship and his/her clinical judgment. In a clinical trial, the investigational device must always be suspect. The degree of certainty of causal relationship of an adverse device effect of either study treatment will be rated as follows:

- **Possible:** An event that might be due to the use of the study device. An alternative explanation - e.g., concomitant drug(s), concomitant disease(s) - is inconclusive. The relationship in time is reasonable; therefore the causal relationship cannot be excluded.
- **Probable:** An event that might be due to the use of the study device. An alternative explanation is less likely - e.g., concomitant drug(s), concomitant disease(s). The relationship in time is suggestive.
- **Definitely:** An event that is due to the use of the study device. The event cannot be reasonably explained by an alternative explanation - e.g., concomitant drug(s), concomitant disease(s).

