8.3.5 TIME PERIOD AND FREQUENCY FOR EVENT ASSESSMENT AND FOLLOW-UP

The occurrence of an ADE may come to the attention of study personnel during study visits and interviews of a study participant presenting for medical care, or upon review by a study monitor.

All ADEs including local and systemic reactions will be captured on the appropriate case report form (CRF). Information to be collected includes the event description, time of onset, clinician's assessment of severity, relationship to study product (assessed only by those with the training and authority to make a diagnosis), and time of resolution/stabilization of the event. All ADEs occurring while in the study will be documented appropriately regardless of relationship. All ADEs will be followed to adequate resolution.

Any medical condition that is present at the time that the participant is screened will be considered as baseline and not reported as an ADE. However, if the study participant's condition deteriorates at any time during the study, it will be recorded as an ADE.

Changes in the severity of an AE will be documented to allow an assessment of the duration of the event at each level of severity to be performed. ADEs characterized as intermittent require documentation of onset and duration of each episode.

The Site Principal Investigator will record all reportable events with start dates occurring from the time of enrollment through the final study visit (Day 84). At each study visit, the investigator will inquire about the occurrence of ADEs since the last visit. Events will be followed for outcome information until resolution or stabilization.

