8.3.6 ADVERSE DEVICE EFFECTS REPORTING

It is understood that complete information about an event may not be known at the time the initial report is submitted. The investigator must assess the relationship of the event to the investigational

device (including rationale for assessment) and should make every attempt to obtain as much information as possible concerning the event. Additional information pertaining to an event should be reported in the EDC as it becomes available.

The investigator must report, via IBM Clinical Development EDC database, all adverse device effects (anticipated or unanticipated) that meet serious criteria occurring from the time of enrollment through the final study visit (Day 84) within 24 hours of knowledge of the event. If the EDC database is temporarily unavailable, the event, including investigator-determined causality assessment, should be reported to DCRI via a paper back-up ADE form. Upon return of the availability of the EDC database, the ADE information must be entered into the eCRF.

The investigator must report, via IBM Clinical Development EDC database, when important follow-up information (final diagnosis, outcome, results of specific investigations, etc.) becomes available after submission of the initial ADE form and information. Follow-up information should be submitted according to the same process used for reporting the initial event as described above (i.e., within 24 hours of knowledge, via IBM Clinical Development EDC database). All adverse device effects will be followed through resolution.

DCRI Safety Surveillance will report all adverse device effects to specified trial personnel (sponsor, protocol principal investigator [PI] and project leader) within 1 to 2 business days of receipt.

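### The protocol contradicts itself on whether adverse events judged unrelated to the device are recorded and reported, and a serious event so judged can have no causality level, no 24-hour route and no serious-event output.

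*Combined protocol and SAP*

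**What the plan says.** The safety sections are written around the adverse device effect. Section 8.3.1: "An ADE is an adverse event related to the use of an investigational medical device". Section 8.2 names ADEs as the content of the safety assessment. Section 8.3.4.2 introduces its causality scale with "The degree of certainty of causal relationship of an adverse device effect of either study treatment will be rated as follows" and then gives three levels: possible, probable and definite. Section 8.3.6 sets a 24-hour duty for "all adverse device effects (anticipated or unanticipated) that meet serious criteria".

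Section 9.4.4 has three outputs:

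- Serious events: "Serious adverse device events for both cohorts will be presented".
- A listing: events judged by site investigators "to be related to the device will be recorded and presented in a listing using the safety population".
- A table: "A tabular summary of adverse events by system organ class and preferred term will also be provided using the safety population".

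Other places are wider. Section 8.3.5: "All ADEs occurring while in the study will be documented appropriately regardless of relationship". The schedule in Section 1.3 has an unqualified adverse-event row from Baseline to Day 84. Section 7.1 requires any adverse event present at discontinuation to be reported and followed, and requires immediate notice to the sponsor when an adverse event causes discontinuation. Section 10.1.8.1 has AEs, not only ADEs, entered in the data-capture system. Section 9.4.5 tabulates or lists reported adverse events with no relatedness condition.

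**The concern.** If relatedness is part of the definition, a rule to document ADEs whatever their relationship has nothing to act on, and a scale with only related levels leaves no way to enter the opposite judgement. A site must choose which half of the protocol to follow, and different sites may choose differently.

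This matters because attribution is hard in this design. The trial is open label, every participant receives AKL-T01, and there is no concurrent control to show a background event rate. All Cohort 1 participants also take a stimulant, and 8.3.4.2 names concomitant drugs and disease as alternative explanations. Headache, nausea and emotional reaction are on the list of expected ADEs in 8.3.3; it is an inference, but a reasonable one, that a site could attribute such events to the stimulant or to the ADHD. A site's causality call should therefore be a recorded variable that others can revisit, not a condition for an event to be seen.

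**Working it through.** No arithmetic applies: the plan states no figure on this point and none can be derived. The check sets the texts side by side and then follows one event through them.

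| Section | Scope as worded | Limited to device-related? |
|---|---|---|
| 8.2 | Safety assessments are ADEs | Yes |
| 8.3.1 | Definition of ADE | Yes, by definition |
| 8.3.4.2 | Three causality levels | Yes; no *not related* level |
| 8.3.5, visit enquiry | ADEs since the last visit | Yes |
| 8.3.6 | 24-hour reporting of serious ADEs | Yes |
| 9.4.4, serious events | Serious adverse device events | Yes |
| 9.4.4, listing | Events the site judges related | Yes |
| 9.4.4, table | Adverse events | None stated; ambiguous |
| 8.3.5, documentation | ADEs, whatever the relationship | No, but contradicts 8.3.1 |
| 8.3.5, deterioration | Worsening of a condition present at screening | No causality test |
| 1.3 | Adverse events, Baseline to Day 84 | No |
| 7.1 | Any adverse event at, or causing, discontinuation | No |
| 9.4.5 | Reported adverse events | No |
| 10.1.8.1 | AEs entered in the data-capture system | No |

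The table in 9.4.4 is ambiguous because the sentence before it says that related events are to be *recorded* as well as listed. That verb can be read as a rule for capture, which would limit what reaches the table, or as loose wording for a listing filter only.

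Now take a serious event that the site judges unrelated and that does not lead to discontinuation.

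1. **Capture.** Sections 1.3 and 10.1.8.1 point to entry. The visit enquiry in 8.3.5 is about ADEs only. Entry depends on which text the site follows.
2. **Causality.** Section 8.3.5 asks for the relationship to be collected, but 8.3.4.2 offers only related levels. The judgement cannot be entered.
3. **24-hour report.** Section 8.3.6 is confined to ADEs and is not triggered. Section 7.1 is not triggered without discontinuation. The unanticipated-problem route in 8.4 needs at least a possible relation to participation in the research, so it does not serve as a general route.
4. **Serious-event output and listing.** Both are worded for device events in 9.4.4. The event is in neither.
5. **Table and 9.4.5 output.** The event appears only if it was captured at step 1.
6. **Second review.** Section 8.3.2 gives the relatedness call for an unanticipated ADE to the sponsor, and 8.3.4.3 gives expectedness to the safety medical monitor. Both act on events sent in, and 8.3.6 obliges sites to send only serious events they have already classed as ADEs.

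If the same event does cause discontinuation, step 3 changes, because 7.1 requires immediate notice. Steps 2 and 4 do not.

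**The case against.** The best reply is that the terms AE and ADE are used loosely and the intention is to record everything. The schedule row, the data-entry text, the discontinuation text, the rule on deterioration and the 9.4.5 output all support this, and the 9.4.4 table on its face already covers adverse events without a filter. Much of this stands, and it rules out several stronger readings that a reader might infer:

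- *Unrelated events have no recording route.* Not supported: Sections 1.3, 7.1, 8.3.5 and 10.1.8.1 give one, though inconsistently.
- *All the safety tables depend on site causality calls.* Not supported: the condition is explicit for the listing and the serious-event output only. The 9.4.4 table is ambiguous, and 9.4.5 has no condition.
- *The event table is the only safety evidence.* Not so: the C-SSRS is repeated at Day 84, reasons for discontinuation are recorded under 7.2, and concomitant medications are tabulated.
- *Incidence is understated by some percentage.* The share of events that sites would judge related is not in the documents, nor is the reading that sites would adopt.

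That site staff know the treatment also adds little by itself, since everyone receives AKL-T01.

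The reply does not remove the core. The section that governs definition, causality and reporting is 8.3, and it is written for ADEs. Section 7.1 sends adverse events to 8.3 under the title of adverse events, and so back to the narrow rules. Section 9 defers further statistical detail to a separate SAP, which could settle the scope of the table but could not add a causality level or recover events never collected.

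**Conclusion.** The point holds as an internal contradiction with one definite consequence. Followed as written, a serious event judged unrelated by the site and not causing discontinuation has no causality level, no stated 24-hour reporting route and no named serious-event output, and the sponsor's relatedness review comes after the site's filter. Whether non-serious unrelated events are recorded and tabulated cannot be settled from the text.

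The size cannot be put as a number. If every site enters all adverse events and sends in all serious ones, nothing is lost beyond the missing causality level and the narrow listing and serious-event output. If sites follow the narrow wording, the loss is whatever they judge unrelated, and it could not be recovered at analysis. The conclusion rests on the wording alone and assumes no rate. It does not touch the efficacy analyses. The correction is worth making because the gap concerns serious events and the cure is cheap.

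**What to change.** Reconcile Sections 8.2, 8.3.1, 8.3.4.2, 8.3.5, 8.3.6 and 9.4.4 with 1.3, 7.1, 9.4.5 and 10.1.8.1 as follows.

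- **8.2, 8.3.1 and 8.3.5:** state that all adverse events from enrolment to Day 84 are asked about and recorded. Keep ADE as the name for the related subset.
- **8.3.4.2:** add a *not related* level.
- **8.3.6:** apply the existing serious-event reporting to all serious adverse events. The criteria for serious are listed only inside the definition of an unanticipated ADE in 8.3.2, so 8.3.6 should point to them.
- **9.4.4:** state that the listing, the serious-event output and the system-organ-class and preferred-term table cover all events, with device-related events shown as a subset.
- **7.1:** correct the title given for Section 8.3 in the cross-reference.

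The cost is protocol wording, one more level on an existing eCRF field, and a few more events for sites to enter and report. The adverse-event row in the schedule is already there.

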9.4.5 DESCRIPTIVE STATISTICS

Tabular outputs and/or listings will be provided at all available timepoints (baseline, Day 28, Day 56, Day 84) for the following outcomes: (1) AKL-T01 and AKL-X01 actual usage; (2) participant preference surveys and questionnaires; (3) participant demographics; (4) reported adverse events; and, (5) concomitant medications.

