1 PROTOCOL SUMMARY

1.1 SYNOPSIS

Title:	Software Treatment for Actively Reducing the Severity of ADHD as Adjunctive Treatment to Stimulant
Phase:	Post Registration Follow Up Trial
Description of Study Intervention & Symptom Tracking:	
Intervention: AKL-T01 is digital therapeutic software for the neuromodulatory treatment of attention and inhibitory control deficits in pediatric patients with attention deficit hyperactivity disorder. AKL-T01 is an investigational medical device known as Software as a Medical Device (SaMD).
 
Symptom Tracking: AKL-X01 (Fengo) is a mobile application (app) that provides a convenience service to caretakers to capture their routine observations of their child's ADHD symptoms and behaviors in a structured format. AKL-X01 (Fengo) captures symptoms data and provides simple graphical displays; it is not an investigational medical device.

Study Description:	
The study aims to enroll (203) participants, with a confirmed diagnosis of ADHD, at approximately 15 sites and will be divided between 2 cohorts; (130) participants will be enrolled in Cohort 1, and (73) participants will be enrolled in Cohort 2.
 
Cohort 1, the primary cohort, will have been stable (adherence to a prescribed medication schedule) on a stimulant medication, but are inadequately managed by the stimulant (in the opinion of the investigator). The stimulant is managed by their own physician for at least 30 days before baseline. This is the "stimulant cohort."
 
Cohort 2, the secondary cohort will have been stable without any stimulant medication for at least 30 days before the baseline. This is the "no stimulant" cohort.
 
For both cohorts, at least 7 and up to 30 days before baseline, participants' caretakers will

begin using AKL-X01 (Fengo) to track their participants' symptoms and behaviors.

During Treatment Phase 1 (Days 1 through 28) participants in Cohort 1 (stimulant) will continue to receive their current stimulant plus the addition of AKL-T01. Participants in Cohort 2 (no stimulant) will only receive AKL-T01. For both cohorts, during this time the caretakers will monitor their child's symptoms daily with AKL-X01.

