During the 1-Month Break (Days 29 through 56) between AKL-T01 treatment phases, participants in Cohort 1 (stimulant) will continue to receive their current stimulant. In both cohorts, AKL-T01 will be suspended during this time. For both cohorts, during this time caretakers will continue to monitor their child's symptoms daily with AKL-X01.

During Treatment Phase 2 (Days 57 through 84), participants in Cohort 1 (stimulant) will continue to receive their current stimulant plus the addition of AKL-T01. Participants in Cohort 2 (no stimulant) will just receive AKL-T01. For both cohorts, during this time the caretakers will monitor their child's symptoms daily with AKL-X01

Objectives:

Primary: To understand the synergistic effects of combining AKL-T01 (with AKL-X01 symptom tracking) as adjunctive treatment to stimulant medication on impairment.

To understand the effects of AKL-T01 (with AKL-X01 symptom tracking) treatment in participants not recently on stimulant medication on impairment.

Secondary: To understand symptom and attentional effects of AKL-T01 (with AKL-X01 symptom tracking) in all participants (both Cohort 1 and Cohort 2).

Exploratory: To understand sustained benefits, through reduction of ADHD impairment and symptoms, following one month of AKL-T01 treatment (with AKL-X01 symptom tracking).

Endpoints:

Primary (Cohort 1, Cohort 2):

- 1) Overall change in clinician-reported Impairment Rating Scale (IRS) "Overall severity of child's problem in functioning and overall need for treatment" score from baseline to Day 28.

Secondary (Cohort 1, Cohort 2):

- 1) Overall change in ADHD-Rating Scale (ADHD-RS) total component score from baseline to Day 28.
- 2) Clinical Global Impression-Improvement (CGI-I) score at Day 28.
- 3) Overall change in Test of Variable Attention-Version 9 (TOVA) attention composite score (ACS) and certain constituent scores, from baseline to Day 28 (the specific constituent scores will be described in the SAP).

Exploratory (Cohort 1, Cohort 2):

- 1) Overall change in clinician-reported IRS "Overall severity of child's problem in functioning and overall need for treatment" score from baseline to Day 56 and from baseline to Day 84.
- 2) Overall change in ADHD-RS total component score from baseline to Day 56 and from baseline to Day 84.
- 3) CGI-I score at Day 56 and at Day 84.
- 4) Overall improvement in TOVA ACS and certain constituent scores, from baseline to Day 56 and from baseline to Day 84.

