4 STUDY DESIGN

4.1 OVERALL DESIGN

This study is a multi-center, open label trial to determine the effect of AKL-T01 treatment (with AKL-X01 mobile app-based symptom tracking) on ADHD symptoms and impairments in children currently on or off stimulant.

Two hundred and three participants (203) at multiple sites will be enrolled into 2 cohorts. 130 participants will be recruited into cohort 1 and 73 participants will be recruited into cohort 2.

Cohort 1 will have been stable** on stimulant(s) for at least 30 days before baseline. At screening (at least 7 and up to 30 days before baseline), participant caregivers will be instructed to download AKL-X01 on to their smartphone. Caregivers will use AKL-X01 for tracking participants' symptoms and behaviors beginning between days -30 and -7, through day 84. During Treatment Phase 1, Days 1 through 28, participants will continue receiving stimulant and will also receive AKL-T01 treatment. During the 1-month treatment pause, Days 29 through 56, participants will continue receiving stimulant but will discontinue AKL-T01. During Treatment Phase 2, Days 57 through 84, participants will continue receiving stimulant and will also receive AKL-T01 treatment.

****Note:** Medication stability is defined as:

- Moderate response on stimulant, but still room for improvement
- Dose unchanged within past 30 days, but other doses have been tried previously without improvement
- Currently taking stimulant, but parent and/or caregiver wishes not to increase dosage for any reason
- Taking consistent stimulant dose on weekdays, but not on weekends

The hypothesis for Cohort 1 is that children receiving stimulant plus AKL-T01 treatment will improve in ADHD symptoms and impairments from Day 0 to Day 28.

Cohort 2 will have been stable without any stimulant for ≥ 30 days before baseline. At screening (at least 7 and up to 30 days before baseline), participant caregivers will be instructed to download AKL-X01 on to their smartphone. Caregivers will use AKL-X01 for tracking participant symptoms and behaviors beginning between days -30 and -7, through day 84. During Treatment Phase 1, Days 1 through 28, participants will receive AKL-T01 treatment. During the 1-month treatment pause, Days 29 through 56, participants will discontinue AKL-T01. During Treatment Phase 2, Days 57 through 84, participants will receive AKL-T01 treatment.

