5.3 LIFESTYLE CONSIDERATIONS

During this study, participants and parents/caregivers will be asked to:

- Remain on an unchanged dosage of stimulant medication (and stimulant booster, if applicable) during participation in the trial, (Cohort 1).
- Refrain from beginning any treatment with medication during participation in the trial, (Cohort 2).
- Complete gameplay of AKL-T01 for 25 minutes (consecutively) per day, for 5 days each week during the treatment periods.
- Return to the in-clinic visits (Day 28 and Day 84) with the iPad Mini (and iPad charger) that was programmed with their AKL-T01 treatment. Note: On Day 28 the clinical site will return the iPad to Akili for the 1 month break period and will receive the same device from Akili in advance of Day 56 for redistribution to the participant for Treatment Phase II.

During this study, parents and/or caregivers of participants are asked to:

- Complete evaluation of the participant's ADHD symptoms daily (5 days per week) using the AKL-X01 smartphone app. Efforts should be made so that the evaluations are completed at the end of each day, to capture behavior(s) from the entire day. All parents and/or caregivers of participants (study-wide) should complete these evaluations at the same time each day.
- Return to the in-clinic visits with their smartphone and demonstrate they are using the AKL-X01 symptom tracker as described above to the study staff.

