9.1 STATISTICAL HYPOTHESES

The aim of the primary objective is to demonstrate a statistically significant difference on mean change in IRS “Overall severity of child’s problem in functioning and overall need for treatment” score, defined for each participant as the score measured on Day 28 minus the score measured at the baseline visit. In both the medicated and non-medicated cohorts, the statistical significance of the primary efficacy analysis will be assessed using a 2-sided paired *t*-test evaluated at the 95% level of confidence. The formulation of the null (H_0) and alternative (H_a) hypotheses are stated below, where μ_d refers to the true mean difference:

- $H_0: \mu_d = 0$
- $H_a: \mu_d \neq 0$.

If, within a particular cohort, the upper bound of the 95% confidence interval around the sample difference is smaller than 0, we will have sufficient evidence to reject H_0 and conclude that AKL-T01 plus Fengo improves ADHD symptoms in that cohort.

If the set of sample differences is non-normal, defined here as skewness larger than 1.5 in magnitude, the efficacy analysis will proceed as a non-parametric Wilcoxon signed rank test. Significance will be determined by evaluating the *W*-statistic at the 95% level of confidence.

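### Fengo symptom ratings span run-in, treatment, break and re-treatment, but only usage is planned for output, while Section 9.1 turns an uncontrolled IRS change into a device effect on symptoms

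*Combined protocol and SAP*

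**What the plan says.** Section 4.1 describes an open-label study with no comparator arm. In both cohorts caregivers use the app for tracking "symptoms and behaviors beginning between days -30 and -7, through day 84". Section 1.1 confirms that tracking goes on in the Day 29 to 56 break, with AKL-T01 suspended: "caretakers will continue to monitor their child's symptoms daily with AKL-X01". Section 5.3 sets the frequency: "symptoms daily (5 days per week) using the AKL-X01 smartphone app". The app records content and not only log-ins; Section 1.1 says that it "captures symptoms data and provides simple graphical displays; it is not an investigational medical device". Section 6.2, on minimising bias, asks for end-of-day entries at a consistent time.

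For output, Sections 1.1 and 3 list AKL-X01 usage against the expected five days a week as a descriptive endpoint, and Section 9.4.5 lists "AKL-T01 and AKL-X01 actual usage". Fengo symptom ratings appear in none of the primary, secondary, interim, tabulation or exploratory lists (Sections 9.4.2, 9.4.3, 9.4.6, 9.4.8, 9.4.9).

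The primary test is a paired t-test on one Day 0 and one Day 28 clinician IRS item, within each cohort. If the upper 95% confidence bound is below zero, Section 9.1 will "conclude that AKL-T01 plus Fengo improves ADHD symptoms in that cohort".

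**The concern.** A single-arm paired change mixes any device effect with a trend already under way, regression to the mean, and caregiver or rater expectancy. Children enter because they are impaired and inadequately controlled, so some fall after entry is plausible without any effect. One baseline value cannot show a trend. The Fengo run-in is the only repeated pre-treatment symptom measurement in the trial, and the break is the only off-treatment period with frequent ratings, yet no summary of the ratings is planned for either.

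The Section 9.1 wording then goes further than the test in two ways. It attributes the change to the product, and it speaks of symptoms although the tested item is overall impairment. A significant result would be reported as a device effect on symptoms with no planned look at whether the trial's own symptom ratings agree.

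**Working it through.** **The plan's own figure.** Section 9.2 reproduces with n = ((1.960 + 1.282)/effect size)². For 0.30 this is 116.7, so 117. For 0.40 it is 65.7, so 66. Dropout: 117/0.9 = 130 and 66/0.9 = 73.3 (plan: 73). The point does not affect these figures.

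**Ratings available per child at 5 per week.**
- Run-in: 7 × 5/7 = 5 to 30 × 5/7 ≈ 21.
- Phase 1, break and Phase 2: 28 × 5/7 = 20 each.
- Total: 65 to about 81.

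**Clinic measurements (Section 1.3).** Clinician IRS, ADHD-RS and TOVA are taken at Day 0, 28, 56 and 84: one value before treatment and one at the end of the break. The parent IRS is taken only at Screening and Day 84.

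**Precision of a Fengo phase contrast.** The documents give no Fengo scale, SD or correlation. Assume a within-child SD of 1, lag-1 correlation 0.3 and SD of true change between children 0.7. All results are in within-child rating SDs.

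*Simple contrast, 5 run-in against 20 Phase 1 ratings.* The autocorrelation factor is 1.3/0.7 = 1.857. Variance per child = 1.857 × (1/5 + 1/20) + 0.49 = 0.954, SD 0.977. SE = 0.977/√117 = 0.09 and 0.977/√66 = 0.12.

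*Contrast net of an extrapolated run-in slope.* Variance per child = Var(run-in mean) + D² × Var(run-in slope) + Var(Phase 1 mean) + 0.49. D is the distance in days from the middle of the run-in ratings to the middle of the Phase 1 ratings. The variances come from generalised least squares with the correlation above.

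| Run-in | D | Variance per child | SE, n = 117 | SE, n = 66 |
|---|---|---|---|---|
| 5 ratings, Days −7 to −3 | 18.5 | 0.317 + 342.25 × 0.117 + 0.089 + 0.49 = 40.9 | 0.59 | 0.79 |
| 5 ratings spread over Days −7 to −1 | 17.5 | 0.317 + 306.25 × 0.052 + 0.089 + 0.49 = 16.8 | 0.38 | 0.50 |
| 21 ratings, Days −30 to −1 | 29 | 0.085 + 841 × 0.00102 + 0.089 + 0.49 = 1.52 | 0.11 | 0.15 |

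Other calendar placements put the 7-day figures at up to about 0.61 and 0.81, and the 30-day figures at about 0.12 and 0.16. Allowing slopes to differ between children would raise all of them. Forcing one common slope across run-in and Phase 1 gives about 0.10 and 0.14, but only by assuming that the trend on treatment equals the trend before it.

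Phase means and contrasts are therefore informative under these assumptions. A slope-adjusted contrast is not, when the run-in is only a week.

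**The case against.** Several points on the other side stand.

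- A reader might infer that no planned analysis follows symptoms on and off treatment. The documents do not support that. Sections 3, 9.4.8 and 9.4.9 plan IRS, ADHD-RS, CGI-I and TOVA at Day 56 and Day 84, by cohort. This is an on/off/on sequence on the named instruments, though with one visit per phase and descriptive only. It says nothing about the period before Day 0.
- A reader might infer that the Fengo ratings are discarded. Section 9 refers to a separate SAP whose text is not included, and it could add an analysis. The deferrals actually named are TOVA constituents, additional primary analyses and subgroups. The supportable statement is that the protocol specifies no such analysis.
- A reader might infer that regression to the mean would by itself produce the planned effects: with selection 1 SD high and test-retest correlation 0.6 to 0.8, the expected fall is (1 − r) × 1 = 0.20 to 0.40 SD, close to 0.30 and 0.40. The match is not established. The stated cut-off is on the parent IRS at Screening, whereas the outcome is the clinician IRS from Day 0. The planned effects are scaled by an assumed SD of 1, which a paired test takes as the SD of change and not of the score. The CGI-S at Day 0 leaves a route for regression, but no threshold is given.
- A reader might infer that run-in against treatment isolates AKL-T01 from tracking. It helps, but the effect of tracking may itself change over time, and expectancy rises when treatment starts.
- The tracker is open label, and the documents define no score and describe no validation. That is a good reason not to make it a condition for the primary claim.

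**Conclusion.** The point holds in limited form. In the text available, symptom ratings collected about five days a week over all four phases have no planned output beyond usage, and no outcome measure can show a trend before Day 1. The Section 9.1 conclusion is stronger than an uncontrolled paired change in an impairment item allows, both in attributing cause and in naming symptoms.

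The gap is one of interpretation. The sample size and the primary test are not in question, and the size of any pre-existing trend or regression to the mean cannot be derived from the documents. A Fengo phase summary could reveal a marked run-in trend or a loss of benefit in the break. It would not replace a control group or remove expectancy. The precision figures rest wholly on the assumed SD, correlation and between-child variation, and are not on the IRS scale.

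**What to change.** 1. In Sections 9.1 and 9.4.2, state the conclusion unconditionally as a change from baseline in IRS overall impairment within an uncontrolled cohort. Do not describe it as an effect of the device on symptoms. Align the matching sentence in the introduction to Section 9.
2. In Section 9.4.5 or 9.4.9, add a supportive analysis per cohort of Fengo symptom ratings by run-in, Phase 1, break and Phase 2:
   - Define the score, the missing-day rule and a minimum number of run-in ratings. Reconcile the run-in limits: Section 1.3 ends Screening at Day −8, and Section 4.1 allows tracking to begin as late as Day −7.
   - Report phase means and contrasts from a mixed model with autocorrelated errors.
   - Show the run-in trend descriptively, and adjust for an extrapolated slope only where the run-in is long enough.
   - Fix the text before the interim look in Section 9.4.6, taken when about 50% of each cohort has Day 28 data.
   - State that the analysis does not gate the primary result.

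The cost is protocol or SAP text, one further analysis, and transfer of coded symptom entries to the study database. The documents describe no such transfer; sites only check entries on the caregiver's phone. No visits, assessments or participants are added. The remaining weakness is that the ratings are unblinded and come from a tracker with no described validation.
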